3.4 Study Design Rationale

3.4.1 AR101 Dose Regimen and Study Periods

The dose regimen in this study is based on the dosing regimen successfully used in the phase 2 studies, ARC001 and ARC002. The ARC001 dosing regimen was based on the work of the Consortium of Food Allergy Research (CoFAR) and its investigators. The basic structure of the dose regimen consists of a 2-day initial escalation at very low doses, followed by an up-dosing phase of dose escalations with a single dose level escalation occurring every 2 weeks, and then an initial maintenance phase followed by an extended maintenance phase. This dosing regimen was well tolerated and effective in previous studies (Burks, 2012), and the 300 mg target dose was well tolerated and had clinically important activity in the AR101 phase 3 studies.

In addition, the dosing regimen to be used in this study in the Maintenance and Extended Maintenance Periods is a 300 mg dose to be administered at the dosing interval that the subject last tolerated in a previous Aimmune-sponsored clinical study.

A follow-up observation period after the last dose of AR101 is included to assess sustained clinical effect of AR101 treatment.

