7.1.3 End of Treatment Visit

At the early discontinuation of AR101 dosing (for subjects who discontinue early) or at the end of AR101 treatment, subjects will return to the clinic for the End of Treatment visit. A DBPCFC (Appendix 11) will be performed for all subjects except those who discontinue early for safety reasons. AR101 will not be administered on the days of the DBPCFC. AR101 dosing will continue until the last food challenge is performed.

The following procedures will be performed before the DBPCFC:

- Monitoring and recording of AEs, including allergic symptoms
- Concomitant medication review
- Food allergen exposure update
- Return of unused AR101
- AR101 dosing compliance check
- Complete physical examination, including weight and height
- Vital signs
- PEF (should be measured at approximately the same time of day at each visit assessment)
- Blood sample collection:
 - CBC (if not completed within prior 6 months)
 - Immunology assessments
- Urine pregnancy test (for sexually active females of childbearing potential only)
- SPT
- PEESS v2.0 (for subjects who had GI AEIs)

- Completion of questionnaires:
 - ACT/C-ACT (for subjects with known asthma only) (before PEF assessment)
 - TNSS (for subjects with known allergic rhinitis only)
 - FAQLQ and FAIM

The following procedures will be performed before discharge from the clinic:

- Monitoring and recording of AEs, including allergic symptoms
- Peanut allergy training

At the end of the End of Treatment visit, the investigator must advise the subject or parent/caregiver of appropriate options for continued management of peanut allergy.

Telephone contact: Site staff will contact the subject or subject's parent/caregiver by telephone at least 14 days after the last AR101 dose or last food challenge, whichever is last, to enquire if any AEs (including allergic symptoms, GI symptoms, and accidental/nonaccidental food allergen exposure) occurred after the subject left the clinic and to provide assistance in management of events.

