3.2. EFFICACY ENDPOINTS

The secondary efficacy endpoints are as follows:

• Proportion of subjects tolerating each challenge dose in the OLFC and the DBPCFC

- The maximum tolerated challenge dose at each food challenge
- Change in tolerated dose of peanut protein
- Maximum severity of symptoms in each food challenge
- Frequency of use of epinephrine as a rescue medication during the food challenges
- Changes in food allergy QoL scores as measured by Food Allergy Quality of Life Questionnaires (FAQLQ), and the Food Allergy Independent Measure (FAIM) questionnaire
- Change in Food Allergy Quality of Life Parental Burden (FAQL-PB) questionnaire score

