9.11. STUDY TREATMENT EXPOSURE

The calculation of exposure will be based on in clinic dosing data and at home dosing as captured on the Study Product Exposure CRF page.

First and last dose dates for each study period are identified as described in Section 7.5.

The total amount of study product consumed will be calculated as the sum of in-clinic doses plus the estimated number of doses taken at home. At-home doses will be estimated by combining the doses across each dosing interval entered on the Study Product Exposure CRF page and taking into account the dosing frequency and any missed and partial doses as captured on the Subject Dosing Diary CRF.

The following calculations of study drug exposure will be made and summarized:

• Duration of Exposure (in days and in years): calculated as the date of last dose of study drug minus the date of the first dose of AR101 plus one during the study

> period, except for the Initial Escalation period, where the duration of exposure will only be 1 or 2 days depending on whether drug was taken on Initial Escalation Day 1 and Initial Escalation Day 2. Duration of exposure will be summarized using descriptive statistics for continuous data as well as categorically by 28-day increments for the first year and by year for the overall treatment periods: \leq 28 days, 29 to 56 days, 57 to 84 days, ..., 1 to < 2 years, 2 to < 3 years, 3 to < 4 years, 4 to < 5 years, and \geq 5 years.

- Total dose consumed (mg): calculated as the cumulative sum of all doses taken during the study period.
- Average dose per day (mg): calculated as the total dose consumed divided by the number of days during the study period.
- Maximum dose achieved (mg/day): summarized using descriptive statistics for continuous data as well as categorically using all possible dose levels: 0.5, 1, 1.5, 3, 6, 12, 20, 40, 80, 120, 160, 200, 240, or 300 mg/day.
- Number of unsuccessful dose increases: calculated as the number of single doses given at the study site at a higher dose level followed by an immediate return to the previous dose level or a lower dose level.
- Number of dose reductions: calculated as the number of any decrease in dose level given at the study site that does not qualify as an unsuccessful dose increase.

Study treatment exposure parameters will be summarized by the following study periods:

- Initial Escalation
- Up-Dosing
- Initial and Extended Maintenance

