Prior medications, concomitant medications, and rescue medications will be summarized separately by ATC Class and generic drug name. Summaries of prior and concomitant medications will include medications from parent studies (ARC002, ARC003, ARC004, ARC005, ARC007, ARC010, and ARC011). Subjects will be counted no more than one time per generic drug name and no more than one time per ATC Level 4.

Rescue medications will be summarized by ATC Class and generic drug for the following study periods:

• Initial Escalation

- Up-Dosing
- Initial and Extended Maintenance (excluding rescue medications taken as a result of an OLFC)
- OLFCs (Total AR101 Exposure < 1 year; 1 to < 2 years; 2 to < 3 years; 3 to < 4 years; 4 to < 5 years; ≥ 5 years)
- DBPCFCs (Total AR101 Exposure < 1 year; 1 to < 2 years; 2 to < 3 years; 3 to < 4 years; 4 to < 5 years; ≥ 5 years)
- Overall, including all rescue medications reported on the CRF

The summary of rescue medications will be repeated for the subgroups described in Section 6.3.

Prior medications and concomitant medications (including medications from parent studies [ARC001, ARC002, ARC003, ARC004, ARC005, ARC007, ARC010, and ARC011]), prior and on-study rescue medications, prior and on-study epinephrine, and concomitant non-drug therapies will be listed by subject.

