10.1. SUBJECTS TOLERATING EACH CHALLENGE DOSE AND THE MTD AT EACH FOOD CHALLENGE

Open-Label Food Challenge

Subjects in Treatment Pathway 5 will have an OLFC at the end of initial maintenance (ie, after an overall total of approximately 12 months of treatment, including initial escalation, up-dosing, and maintenance). The OLFC is adapted for young children based on accepted food challenge procedures. During the OLFC at the end of initial maintenance, single doses of peanut protein (3, 10, 30, 100, 300, 600, 1000, and 2000 mg) will be conditionally tested using a food challenge mixture administered sequentially at 20- to 30-minute intervals.

Subjects in Treatment Pathways 4 and 5 will have an OLFC after completing 12 months of Extended Maintenance treatment and may participate in an optional OLFC yearly thereafter and at the End of Treatment visit. Subjects in Treatment Pathways 1, 2, and 3 may participate in an optional yearly OLFC during the Extended Maintenance Period (ie, after completing 12 months of Extended Maintenance treatment and yearly thereafter) and the End of Treatment visit OLFC to assess the level of desensitization to peanut protein. Each OLFC during the Extended Maintenance Period will be conducted over a single day and in keeping with accepted food challenge procedures, will conditionally test 4 unblinded single doses sequentially at 20- to 30-minute intervals: 300 mg, 600 mg, 1000 mg, and 2000 mg of peanut protein using a defatted peanut flour.

OLFC data and derived desensitization response at each OLFC will be listed by treatment pathway and subject ID.

Double-Blind, Placebo-Controlled Food Challenge

A DBPCFC will be performed at the End of Treatment visit; subjects who discontinue AR101 treatment early for safety reasons will not have the DBPCFC. An optional DBPCFC will be performed after approximately 1 year of follow-up observation.

Each DBPCFC will be conducted over 2 days and consistent with accepted food challenge procedures. Single doses of peanut protein and placebo will be conditionally tested at the DBPCFC (3, 10, 30, 100, 300, 600, 1000, and 2000 mg) using a food challenge mixture administered sequentially at 20- to 30-minute intervals up to a single highest challenge dose of 2000 mg (4043 mg cumulative).

DBPCFC data and derived desensitization response at each DBPCFC will be listed by treatment pathway and subject ID.

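### SAP 9.12 does not split DBPCFC rescue epinephrine by visit, so on its plain reading the endpoint's only specified summary table combines End of Treatment with Study Exit

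*SAP*

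**What the plan says.** SAP 3.2 names as a secondary efficacy endpoint "Frequency of use of epinephrine as a rescue medication during the food challenges". SAP section 10 has no subsection for it. The summary that covers it is the rescue-medication table in SAP 9.12, where one of the headings is "DBPCFCs (Total AR101 Exposure < 1 year; 1 to < 2 years; 2 to < 3 years; 3 to < 4 years", continuing with 4 to under 5 years and 5 years or more. The counting rule in the same section is "Subjects will be counted no more than one time per generic drug name and no more than one time per ATC Level 4".

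There are two DBPCFCs (SAP 10.1). For the first, "A DBPCFC will be performed at the End of Treatment visit", and Protocol 7.1.3 states that "AR101 dosing will continue until the last food challenge is performed"; the sections for the other pathways say the same in substance. For the second, "An optional DBPCFC will be performed after approximately 1 year of follow-up observation".

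Protocol 3.4.1 explains why the later challenge exists: "A follow-up observation period after the last dose of AR101 is included to assess sustained clinical effect of AR101 treatment". SAP 9.11 defines duration of exposure as "calculated as the date of last dose of study drug minus the date of the first dose of AR101 plus one during the study" (within a study period), and also provides a version that includes the parent studies.

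**The concern.** The two challenges answer different questions. The first measures reactivity at the end of continuous dosing. The second measures it about a year after study AR101 stopped. Protocol 3.4.2 gives them separate purposes: desensitization after longer-term dosing, and continued desensitization after follow-up.

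If both feed one set of DBPCFC counts, a reader of the table gets neither figure. The endpoint sits under the objective of desensitization achievable with extended maintenance dosing, and a challenge a year later does not measure that. The comparison of the two visits, which bears on the stated reason for the follow-up year, is also not visible in any planned table.

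**Working it through.** The documents state no epinephrine rate, no exit-challenge uptake and no sample size calculation, so there is no figure of the plan's own to reproduce. The check is textual, followed by an illustration.

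**Step 1. Does anything in the SAP 9.12 table separate the two visits?**
- *Heading.* It is plural and names no visit. No Follow-Up Observation heading is listed that could take the Study Exit use.
- *Exposure bands.* Under SAP 9.11, exposure ends at the last dose of study drug. It does not grow during follow-up, so a subject is in the same band at both challenges.
- *Counting rule.* A subject who receives epinephrine at both challenges contributes one count.
- *Subgroup repeats (SAP 6.3).* These are by pathway group and by daily or non-daily regimen, not by visit.

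**Step 2. Does another planned summary cover the endpoint?**
- SAP 9.1 leaves food-challenge symptoms out of the treatment-emergent adverse event summaries.
- SAP 9.2 leaves epinephrine used for food challenges out of its adverse-event-of-interest summary.
- SAP 9.2.1 leaves out anaphylactic reactions during or related to a food challenge.
- SAP 10.2 only lists maximum severity at each challenge.
- SAP 13 does not include this endpoint among those reduced to listings.

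The SAP 9.12 table is therefore the only summary specified. SAP 10.1, by contrast, expressly restricts its tolerated-dose summary to the End of Treatment DBPCFC.

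**Step 3. What could combining do to the figure?** All rates here are assumed. Let p be the proportion using epinephrine at End of Treatment, q the proportion at Study Exit among those challenged there, and f the fraction who return for the exit challenge. The denominator is subjects with an End of Treatment DBPCFC. Returners are assumed to have had that challenge and to share the rate p.

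Combined, once per subject = p + f·q − f·o, where o is the proportion of returners who use epinephrine at both. Complete overlap gives o = min(p, q); independence gives o = p·q. I take these as the range, because use at two challenges in one subject is unlikely to be negatively associated.

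| p, q, f | Complete overlap | Independence |
|---|---|---|
| 5%, 20%, 30% | 0.05 + 0.06 − 0.015 = 9.5% | 0.05 + 0.06 − 0.003 = 10.7% |
| 5%, 20%, 50% | 0.05 + 0.10 − 0.025 = 12.5% | 0.05 + 0.10 − 0.005 = 14.5% |
| 5%, 5%, 50% | 0.05 + 0.025 − 0.025 = 5.0% | 0.05 + 0.025 − 0.00125 = 7.4% |
| 5%, 15%, 50% | 0.05 + 0.075 − 0.025 = 10.0% | 0.05 + 0.075 − 0.00375 = 12.1% |
| 10%, 10%, 50% | 0.10 + 0.05 − 0.05 = 10.0% | 0.10 + 0.05 − 0.005 = 14.5% |

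The last two rows matter most. Under complete overlap, a combined 10.0% arises both from a threefold rise after stopping (5% to 15%) and from no change at all (10% at both visits). The table alone could not tell these apart.

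**The case against.** The strongest reply is that SAP 9.12 is silent on visit rather than committed to pooling. SAP 10.1 presents the End of Treatment DBPCFC by the same kind of exposure years, so SAP 9.12 may mean that challenge only. The table shells (SAP 18) are not among these documents and could settle it. This stands as a limit on certainty. It does not remove the gap, because the text as written covers every DBPCFC.

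A reader might infer more than the documents support in four ways.
- *That the two challenges cannot be separated.* On-study epinephrine and the data from each DBPCFC are to be listed by subject (SAP 9.12 and 10.1), and listings carry study-period flags and visit labels (SAP 7.2). A by-visit count can be made from these, so the limitation is in the summary table.
- *That an End of Treatment figure is overstated.* No figure in SAP 9.12 carries that label. A combined total would be correct as a total, only hard to interpret.
- *That Study Exit shows reactivity off treatment.* During follow-up a subject may use commercial product, food equivalents or other investigational immunotherapy (SAP 2.4.2.7). A visit split alone does not isolate an untreated state.
- *That the OLFC rows have the same defect.* OLFCs are yearly and on treatment, so exposure advances between them and the argument from fixed exposure does not apply.

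It is also fair to say that no formal comparison of the two visits is planned (Protocol 9.2, SAP 6.4), so no promised analysis is lost.

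**Conclusion.** The point holds for the summary table. Followed as written, SAP 9.12 combines DBPCFC rescue use at End of Treatment with use about 12 months after the last dose, and neither the exposure bands nor the counting rule restores the split.

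The size cannot be established from the documents. The 9.5% to 14.5% against an assumed 5% at End of Treatment depends on the chosen exit rate of 20%, uptake of 30% to 50%, and the overlap of users. Lower uptake moves the combined figure towards the End of Treatment rate. In a descriptive study with the underlying data listed, this is a worthwhile and cheap improvement to a named secondary endpoint. It does not undermine the trial's primary safety description.

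**What to change.** Report DBPCFC rescue epinephrine in two blocks, End of Treatment and Study Exit. In each, use as denominator the number of subjects challenged at that visit (and in that exposure band), and count each subject once per drug per challenge. Show the Study Exit block also by treatment plan during follow-up, which is collected at the telephone contacts and at the exit visit.

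Label the added table post hoc. SAP 1.1 states that Version 2 was prepared after database lock with changes confined to Appendix A, and SAP 6.1 requires additional analyses to be identified as post hoc and exploratory. The cost is a few extra rows and the programming for them; no new data are needed. If the table shells already restrict the heading to one visit, it is enough to say so in the study report and add the Study Exit block.

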10. ANALYSIS OF EFFICACY ENDPOINTS

Unless otherwise noted, efficacy data will be summarized descriptively, and the Safety Population will be used for all summaries of efficacy parameters. Efficacy listings will include all enrolled subjects, sorted by treatment pathway.

10.1. SUBJECTS TOLERATING EACH CHALLENGE DOSE AND THE MTD AT EACH FOOD CHALLENGE

Open-Label Food Challenge

Subjects in Treatment Pathway 5 will have an OLFC at the end of initial maintenance (ie, after an overall total of approximately 12 months of treatment, including initial escalation, up-dosing, and maintenance). The OLFC is adapted for young children based on accepted food challenge procedures. During the OLFC at the end of initial maintenance, single doses of peanut protein (3, 10, 30, 100, 300, 600, 1000, and 2000 mg) will be conditionally tested using a food challenge mixture administered sequentially at 20- to 30-minute intervals.

Subjects in Treatment Pathways 4 and 5 will have an OLFC after completing 12 months of Extended Maintenance treatment and may participate in an optional OLFC yearly thereafter and at the End of Treatment visit. Subjects in Treatment Pathways 1, 2, and 3 may participate in an optional yearly OLFC during the Extended Maintenance Period (ie, after completing 12 months of Extended Maintenance treatment and yearly thereafter) and the End of Treatment visit OLFC to assess the level of desensitization to peanut protein. Each OLFC during the Extended Maintenance Period will be conducted over a single day and in keeping with accepted food challenge procedures, will conditionally test 4 unblinded single doses sequentially at 20- to 30-minute intervals: 300 mg, 600 mg, 1000 mg, and 2000 mg of peanut protein using a defatted peanut flour.

OLFC data and derived desensitization response at each OLFC will be listed by treatment pathway and subject ID.

Double-Blind, Placebo-Controlled Food Challenge

A DBPCFC will be performed at the End of Treatment visit; subjects who discontinue AR101 treatment early for safety reasons will not have the DBPCFC. An optional DBPCFC will be performed after approximately 1 year of follow-up observation.

Each DBPCFC will be conducted over 2 days and consistent with accepted food challenge procedures. Single doses of peanut protein and placebo will be conditionally tested at the DBPCFC (3, 10, 30, 100, 300, 600, 1000, and 2000 mg) using a food challenge mixture administered sequentially at 20- to 30-minute intervals up to a single highest challenge dose of 2000 mg (4043 mg cumulative).

DBPCFC data and derived desensitization response at each DBPCFC will be listed by treatment pathway and subject ID.

For each OLFC and DBPCFC at End of Treatment, the proportion of subjects who tolerate each challenge dose (3 mg, 10 mg, 30 mg, 100 mg, 300 mg, 600 mg, 1000 mg, and 2000 mg) of peanut protein with no more than mild allergy symptoms will be assessed using the Safety Population. Desensitization response rates and associated 95% CIs will be presented using exact Clopper Pearson CIs. The number and percentage of subjects at each dose level for MTD will also be summarized. Summaries for the OLFCs will be presented at each time point (End of Initial Maintenance, Extended Maintenance every year) and by years of total AR101 exposure (including parent studies) and overall. A summary of the DBPCFC at End of Treatment will be presented for each treatment pathway by years of total AR101 exposure and overall.

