3.2.5 Extended Maintenance Period (All Treatment Pathways)

The last treatment period for all treatment pathways is the Extended Maintenance Period. Subjects who completed initial maintenance in the parent AR101 study (Treatment Pathways 1 and 4) will enter the Extended Maintenance Period after the Screening/Baseline visit, and the other subjects (Treatment Pathways 2, 3, and 5) will enter the Extended Maintenance Period after completing the Initial Maintenance Period in this study, after completing both the Repeat Up-Dosing and Initial Maintenance Periods in their parent study, or after receiving AR101 300 mg OD for at least 24 weeks in their parent study.

During the Extended Maintenance Period, subjects will continue their current dosing regimen (300 mg QD, BIW, QW, or QOW) so long as they continue to tolerate it. At any point during ARC008, subjects on nondaily dosing regimens may switch to Treatment Pathway 2 and enter Repeat Up-Dosing if they do not tolerate nondaily dosing.

For subjects continuing nondaily dosing, the dosing intervals should be as consistent as possible, preferably on the same day(s) each week.

- For BIW dosing regimen, doses should be at least 3 days apart (eg, Monday and Thursday each week)
- For QW dosing regimen, doses should be taken on the same day (±1 day) each week

- ARC008 Protocol Amend 6.0
- For QOW dosing regimen, doses should be taken on the same day (±2 days), every alternate week
- Study visits will occur approximately every 3 months until the study ends (Section 3.6).

Subjects in Treatment Pathways 1, 2, and 3 who enter this period will have the option to participate in an OLFC to assess level of desensitization to peanut protein after 12 months in the Extended Maintenance Period and yearly thereafter. For subjects in Treatment Pathways 4 and 5, the OLFC after the first 12 months of extended maintenance treatment is required and then optional yearly thereafter.

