6.2.3 Double-Blind, Placebo-Controlled Food Challenge

A DBPCFC will be performed at the End of Treatment visit; subjects who discontinue AR101 treatment early for safety reasons will not have the DBPCFC. An optional DBPCFC will be performed after approximately 1 year of follow-up observation.

Each DBPCFC will be conducted over 2 days and consistent with accepted food challenge procedures. Single doses of peanut protein and placebo will be conditionally tested at the DBPCFC (3, 10, 30, 100, 300, 600, 1000, and 2000 mg) using a food challenge mixture administered sequentially at 20- to 30-minute intervals up to a single highest challenge dose of 2000 mg (4043 mg cumulative).

The DBPCFC is described in detail in Appendix 11, including all requirements before, during, and after the DBPCFC. Subjects with allergy to oat or rice will not have the DBPCFC. Full details are provided in the study procedures manual.

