4. ANALYSIS POPULATION

The following analysis population will be defined for this study:

Safety Population: The Safety Population will consist of all subjects who receive AR101 during ARC008. The Safety Population will be used for all analyses.

5. **PROTOCOL DEVIATIONS**

Any change, divergence, or departure from the study design or procedures constitutes a protocol deviation. All protocol deviations will be reported on a specific case report form (CRF) as follows:

- Inclusion Criteria
- Exclusion Criteria
- Received Incorrect Study Treatment
- Informed Consent Form (ICF)
- SAE Not Reported
- Visit Out Of Window
- Missed Study Visit
- Procedure Not Per Protocol
- Prohibited Concomitant Medication
- Lab Sample Missed
- Study Drug Compliance
- Other, Specify

These protocol deviations will be reviewed prior to database lock and their categorization as major or minor will be determined prior to database lock. All protocol deviations, both major and non-major, will be listed and included in the study report.

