6. GENERAL ASPECTS FOR STATISTICAL ANALYSIS

6.1. STATISTICAL NOTATION AND METHODOLOGY

Unless otherwise stated, the term "descriptive statistics" refers to the number of subjects (n), mean, median, standard deviation, minimum, and maximum for continuous variables and frequencies and percentages for categorical variables.

Unless specified otherwise, the denominator for percentages for categorical data will be based on the number of subjects or observations with non-missing data appropriate for summary purposes. The denominator for percentages for incidence data (such as AEs) will be based on the number of subjects in the analysis population "at risk". Select ordinal data may be summarized using both descriptive statistics and counts and percentages of subjects in each category, as appropriate.

Minimum and maximum values will be presented at the precision of the original value, means and medians will be rounded to 1 decimal place greater than the precision of the original value, standard deviations and standard errors will be rounded to 2 decimal places greater than the precision of the original value. Percentages will be rounded to 1 decimal place. Percentages that round down to 0 or up to 100% will be displayed as "<0.1%" and ">99.9%", respectively. Other statistics (e.g., confidence intervals [CIs]) will be presented using the same general rules outlined above or assessed for the most appropriate presentation based on the underlying data.

Unless otherwise noted, values reported as greater than or less than some quantifiable limit (e.g., "< 1.0") will be summarized with the sign suppressed in summary tables and figures, using the numeric value reported. Data will display on subject listings to include the sign.

In general, summary tables will be presented by combining subjects from each of the treatment pathways into a single treatment group (AR101).

All relevant data collected in the database and any derived data will be included in data listings and unless otherwise noted sorted by treatment pathway, subject ID, test/measurement, and visit and time point as appropriate.

All statistical methods will be based on the International Conference on Harmonisation (ICH)-E9 Guidance for Industry "Statistical Principles for Clinical Trials".

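### SAP 10.1 does not fix the denominator for food-challenge response rates; one reading omits safety stops from the End of Treatment DBPCFC, and the OLFC summaries pool required with optional participants

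*SAP*

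**What the plan says.** SAP 10.1 plans response rates with exact Clopper-Pearson 95% intervals at eight doses from 3 to 2000 mg, for each OLFC and for the End of Treatment DBPCFC. The proportion tolerating each dose "of peanut protein with no more than mild allergy symptoms will be assessed using the Safety Population". SAP 4 defines that set broadly: "The Safety Population will consist of all subjects who receive AR101 during ARC008".

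SAP 6.1 gives the general rule, which applies unless something else is specified: "the denominator for percentages for categorical data will be based on the number of subjects or observations with non-missing data appropriate for summary purposes".

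Not everyone in the Safety Population has a challenge result:

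- End of Treatment DBPCFC (Protocol 6.2.3): "subjects who discontinue AR101 treatment early for safety reasons will not have the DBPCFC". Also, "Subjects with allergy to oat or rice will not have the DBPCFC".
- OLFC in Pathways 1-3 (SAP 10.1): these subjects "may participate in an optional yearly OLFC during the Extended Maintenance Period".
- OLFC in Pathways 4 and 5 (Protocol 3.2.5): "For subjects in Treatment Pathways 4 and 5, the OLFC after the first 12 months of extended maintenance treatment is required". Later yearly OLFCs are optional for them too.

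OLFCs during Extended Maintenance test only 300, 600, 1000 and 2000 mg. SAP 10.1 breaks the DBPCFC summary down by treatment pathway but says nothing similar for the OLFC summaries. The general convention in SAP 6.1, which combines all pathways into one AR101 group, therefore applies to them.

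**The concern.** Different programmers could follow SAP 10.1 and report different rates from the same data, because the divisor is not stated.

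The choice also bears on interpretation. Some subjects lack a DBPCFC result for a reason tied to how they fared on treatment: they were stopped for safety. Others lack a challenge result for reasons that need have nothing to do with tolerance, such as oat or rice allergy or not taking up an optional OLFC. Leaving out the first group gives a rate among those who stayed on treatment and were challenged. Counting the second group as failures understates tolerance. A reader of the table could not tell which had been done.

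The OLFC summaries raise a separate problem. Results over successive years invite reading as the course of desensitization. If the balance of required and voluntary participants changes after the first year, the pooled rate can move for that reason alone.

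**Working it through.** The documents state no expected response rate, dropout or sample-size calculation, so there is no planned figure to reproduce. The check sets the readings side by side and then illustrates their spread on assumed inputs.

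**Reading A: the Safety Population is the denominator.** Anyone not challenged counts as not tolerating. At 3, 10, 30 and 100 mg in an Extended Maintenance OLFC no dose is given. If tolerating a dose requires receiving it, the rate there is 0% by construction.

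**Reading B: the non-missing rule applies within the Safety Population.** Subjects stopped for safety have no End of Treatment DBPCFC, and SAP 7.5 imputes only a missing symptom severity within a challenge, not an absent challenge. They leave the denominator. At 3-100 mg in an Extended Maintenance OLFC the denominator is empty.

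**Direction.** Let r be responders, n subjects challenged and s subjects stopped for safety.

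- Rate among challenged: r/n.
- Rate with safety stops as not tolerating: r/(n+s).
- Gap: (r/n) × s/(n+s), which is above zero whenever r and s are above zero.

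**Illustration at 1000 mg.** N = 950 is the approximate potential enrolment in Protocol 3.5. The 65% tolerating is borrowed from the ARC002 figure in Protocol 3.4.2. The other inputs are assumptions: 10% stopped for safety (95) and 20% unchallenged for other reasons (190). That leaves 950 − 95 − 190 = 665 challenged and 432 responders.

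| Denominator | Rate | Exact 95% CI |
|---|---|---|
| Challenged | 432/665 = 65.0% | 61.2-68.6 |
| Challenged plus safety stops | 432/760 = 56.8% | 53.2-60.4 |
| Full Safety Population | 432/950 = 45.5% | 42.3-48.7 |

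**Range of the safety-stop gap.** With nobody else unchallenged, 5%, 10% or 20% stopped turns 65.0% into 61.7%, 58.5% or 52.0%, a gap of 3 to 13 points. With 20% stopped and 40% unchallenged for other reasons, it is 65.0% against 247/570 = 43.3%, about 22 points. Across 5-20% stopped and 0-40% otherwise unchallenged, the full Safety Population rate runs from 61.7% down to 26.0%.

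**OLFC mix (all inputs assumed).** Hold true rates constant at 90% in Pathways 4-5 and 70% in Pathways 1-3.

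- 100 and 150 participants: (100×0.9 + 150×0.7)/250 = 195/250 = 78%.
- 30 and 120 participants: (30×0.9 + 120×0.7)/150 = 111/150 = 74%.

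The pooled rate falls 4 points with no change in either group.

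**The case against.** Several points on the other side stand.

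- A reader might infer that SAP 10.1 and 6.1 contradict each other. They do not. Section 6.1 yields to specific text, and an analysis set is compatible with a non-missing denominator inside it. The matter is unresolved, not contradictory.
- A reader might infer that subjects who stop at a low dose drop out of the rates at higher doses. No text says so. SAP 7.3 defines the MTD per challenge; if response follows it, early stoppers stay in as not tolerating. SAP 10.1 simply does not say that response is derived this way.
- A reader might infer that the plan hides safety stops, or that these rates and the MTD distribution are the only tabulated desensitization results. Neither holds. SAP 8.1 and 9.1 summarize discontinuation reasons and adverse events leading to discontinuation. SAP 9.12 tabulates rescue medication at OLFCs and DBPCFCs, and epinephrine use at challenges is a desensitization endpoint.
- Counting safety stops as not tolerating is a choice of estimand. A stop for chronic gastrointestinal events, for example, is not a measured challenge failure. This is why the line proposed below is supplementary.
- The effect need not exceed sampling error. With 5% stopped, the 3.3-point gap is smaller than the 6.3-point interval width at 902 challenged; at 100 subjects the width is about 19 points. The 4-point OLFC shift is smaller than the exact interval widths of 10.6 points (n = 250) and 14.6 points (n = 150).
- The table shells are a separate document (SAP 18) and may state denominators.

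None of this supplies the missing rule in the SAP, brings safety stops into any DBPCFC rate under the non-missing reading, or separates the pathways in the OLFC summaries.

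**Conclusion.** The point holds as an unresolved denominator with two specific consequences. First, under the non-missing reading, the End of Treatment DBPCFC rate describes only subjects who were challenged, and it exceeds the rate that counts safety stops as not tolerating. The direction is certain once there is at least one responder and one safety stop; the size cannot be computed from the documents. The illustrative 3 to 13 points, or up to about 22 with heavy non-challenge for other reasons, rest on assumed proportions. Whether this should be called inflation depends on the estimand. Second, pooled OLFC rates across years are open to confounding by pathway mix, again of unknown size.

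The full Safety Population is not a safe remedy, since it treats subjects who did not take up an optional challenge, or could not have one, as failures. The endpoint is secondary and the analysis descriptive, so no test or error rate is affected. The change is still worth making because these rates carry the interval estimates of dose tolerance.

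**What to change.** 1. In SAP 10.1, state that the denominator for each challenge is the Safety Population subjects who started it. Derive response from the MTD in SAP 7.3, so that doses above the stopping dose count as not tolerated. Report only the dose levels that the challenge tests.
2. For the End of Treatment DBPCFC, add a supplementary line that also counts subjects stopped for safety as not tolerating. Show the number not challenged by reason (safety stop, oat or rice allergy, other).
3. Present OLFC tables separately for Pathways 1-3, 4 and 5. SAP 6.3 already uses this grouping for immunoglobulins.

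The cost is SAP wording and a few table rows. Cells become smaller and intervals wider, and the supplementary rate may look less favourable. SAP 1.1 says that Version 2 follows database lock and is restricted to Appendix A, so any analysis added now should be labelled post hoc, as SAP 6.1 provides for additional analyses.
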